## **13. Dissemination Plan**

Results from this study will be collected into a report and will be shared with MOH and the DPS-Z and other key stakeholders. The results will also be disseminated to government officials and health care workers working in these communities. If results are deemed by the authors to be potentially of interest to a wider scientific audience, we would plan on sharing these data in manuscript form, after obtaining appropriate clearances.

## **14. Budget**

	unit cost	#	units		
HUMAN RESOURCES					
Research officer	MZN 50,000.00	1	7	MZN 350,000.00	\$ 5,556
Research assistants (surveyors)	MZN 20,000.00	2	8	MZN 320,000.00	\$ 5,079
TRAVEL & TRANSPORT					
MPT staff travel to Quelimane					

Travel to Quelimane from Maputo (2ps C-Saúde + 1 MOH); 2 trips	MZN 40,000.00	3	2	MZN 240,000.00	\$ 3,810
Per diem Maputo teams on professional travels in MPT/QUEL	MZN 1,400.00	2	12	MZN 33,600.00	\$ 533
Accommodation Maputo teams on professional travels in MPT/QUEL	MZN 5,000.00	2	12	MZN 120,000.00	\$ 1,905
Per diem MOH staff to Zambezia	MZN 6,000.00	1	12	MZN 72,000.00	\$ 1,143
Per diem DPS staff to sites for supervision	MZN 6,000.00	1	10	MZN 60,000.00	\$ 952
Transport interviewers to sites	MZN 9,800.00	1	30	MZN 294,000.00	\$ 4,667
TRAINING/PROJECT ACTIVITIES					
Training Sessions in Intervention Sites					
Food incentives for trainees	MZN 240.00	10	5	MZN 12,000.00	\$ 190
Training Materials	MZN 15,000.00	1	1	MZN 15,000.00	\$ 238
Incentives for MISAU Psychologists					\$ -
Training stipend/per diem	MZN 850.00	1	5	MZN 4,250.00	\$ 67
OTHER					
Tablets	MZN 21,000.00	1	4	MZN 84,000.00	\$ 1,333
Bioethics Review Fees	MZN 20,000.00	1	1	MZN 20,000.00	\$ 317
Transcription of interviews	MZN 3,000.00	1	30	MZN 90,000.00	\$ 1,429
Translation of protocol/ interviews	MZN 20,000.00	1	1	MZN 20,000.00	\$ 317
Surgical Masks	MZN 50.00	1	400	MZN 20,000.00	\$ 317
Snack for sessions	MZN 240.00	400	3	MZN 288,000.00	\$ 4,571
TOTAL COSTS				MZN 2,042,850.00	\$ 32,426

## 15. Timeline

Time (month)	Activities/Description
Month 1	Recruit health care workers from four health facilities (n=100).

Month 1	Among HCW , assess baseline measures of (1) Resilience (2) Stigma (3) Burnout (4) Depersonalization (5) Moral Injury Questionnaire		
Months 1-4	Resilience/Wellness Intervention arm sessions; held bi-monthly	Resilience/Wellness and anti-stigma arm sessions, held bi-monthly	Anti-stigma arm intervention only sessions; held bi-monthly
Months 1-2 & Months 6-7	Recruit a sub-group of PLHIV patients receiving any HIV care and treatment into the study at the four study sites (total n=320) to assess impact of the interventions on medical mistrust, patient satisfaction, and perceived stigma from health care providers via baseline (study start) and end-line (approximately 6 months after study start) surveys.		
Months 1-12	Collect routine clinical data (retention, viral load) from all patients enrolled in care and treatment at the four study sites (n estimated approximately to be 16,000).		
Months 5-7	Among HCW , collect post-intervention surveys (repeat same measures as used at baseline, except for #5 Moral Injury Questionnaire) at all sites (control and intervention).		
Months 8-9	Recruit a sub-group of HCW participants at the three intervention sites for in-depth interviews related to moral injury/ moral trauma.		
Months 8-14	Conduct data analysis of survey outcomes among PLHIV and HCW.		
Months 10-11	Conduct surveys to assess depression, anxiety, and suicidality		
Months 12-15	Conduct data analysis of clinical outcomes among PLHIV.		
Months 12-18	Disseminate findings via community meetings with community members and clinicians		

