#### Wellness and Resilience Intervention

Health care workers working at sites randomized to resilience training or the combination anti-stigma and resilience training will receive a group-based Mindfulness-based Wellness and Resilience (MBWR) intervention. The training course will occur every other week and consist of 4 sessions of 60-120 minutes each. The day and time of the intervention session will be determined by health facility staff to facilitate attendance. We will focus on common challenges encountered in the health facility, as well as coping strategies, and future goals to improve provider well-being.

The team selected a group-based, mindfulness-based wellness and resilience (MBWR) intervention. MBWR is designed to be a brief, cost-effective, evidence-based, and replicable intervention to enhance resilience and self-compassion among teams providing primary health care services. The training is based on an established Mindful Practice curriculum^63 and Mindfulness-Based Stress Reduction curriculum. This intervention was selected because it focuses on developing resilience and self-care at the team level (which is how HIV care and treatment is delivered) and because the training can be conducted by a trained Bachelor-level psychologist. The original training course consists of weekly sessions of 60-120 minutes each over 6-10 weeks. Our team has adapted the curriculum to include common challenges encountered in these health facilities, facility-level strategies that can empower health care workers to improve conditions, individual coping strategies, and future goals to improve HCW well-being (see **Table 2**).

**Table 2:** Adapted Wellness and Resilience Training Topics

Focus of Resilience Training Sessions	Intended Learning outcomes
1) Burnout and its consequences and ways to respond/ when to seek care	
 
Factors that may lead to the feeling/ experience of burnout;
 
Understand the signs and symptoms of burn-out and the consequences of not-identified burn-out among health care workers;
 
Getting skills to help colleagues in identifying symptoms;
 
Know how to recognize burnout and where to refer to if experiencing symptoms;
 
Interactive component: share ways that burnout impacts either yourself or colleagues who you work with.
 

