#### Anti-Stigma Intervention

Health care workers working at sites randomized to the anti-stigma only or the combination anti-stigma and resilience arm will receive anti-stigma training sessions to address issues with multiple stigmas that may be impacting their ability to provide quality care for PLHIV in Mozambique. The training will occur once every other week, for at least 4 sessions of 60-120 minutes each. The day and time of the intervention session will be determined by health facility staff to facilitate attendance.

Study personnel will work with health care workers at study sites to combine and adapt the most applicable components from three evidence-based anti-stigma interventions. These interventions were selected because: i) they were developed in low and middle income settings (and parts of one intervention have been tested in Mozambique through International Association of Providers of AIDS Care [IAPAC] modules), ii) their focus is on identifying HIV-related and other intersecting stigmas, the impact stigma has on patients, the impact stigmatized beliefs have on health care providers, and iii) they propose ways to create a stigma-free environment in the health setting (see **Table 3**).

**Table 3:** Adapted Anti-Stigma Sessions

Title of exercise/session	Intended learning outcomes
1. Naming stigma through pictures/defining stigma; describing the different types of stigma; consequences of stigma	
 
Participants discuss what similar stigma takes place in different contexts and start to share stories of what they have personally witnessed.
 
Recognition of how personal attitudes and beliefs influence stigmatizing behavior.
 
Helps participants to recognize the causes of stigma and how the resulting effects are manifested.
 
Interactive component: brainstorming as a group the types of and expressions of stigma in the workplace.
 

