## **Procedures for Patients living with HIV**

### *Procedures for PLHIV who have agreed to participate in the survey.*

Survey administration with PLHIV participants enrolled in the study will be completed at two time points: one at baseline (i.e., study initiation) and one at endline (i.e., at 6-7 months after study initiation), including sociodemographic data and three questionnaire components related to: Medical Mistrust, Patient Satisfaction, and Perceived stigma from Health care Providers (**Appendix 2**). The survey will be done at the health facility or at a location suggested by the participant as per the participant's preference, at a location where privacy can be guaranteed as much as possible with the support from a surveyor who is fluent in Echuabo (local language). Participants may be recruited for more than one survey time point, however, different PLHIV participants can be recruited at the two time points. Participants will be requested to allow the use of the Moral Trauma Protocol, Version 1.3; PI: [name], 27 September 2024

of a subset of data related to their ART medication pick-up history for the past 6 months will be collected from their medical records for use in analyzing the survey data (**Appendix 10**). These data will be extracted from the electronic patient tracking system OpenMRS™, which stores clinical information from the medical records of PLHIV registered at the health facility.

*Procedures for PLHIV for whom we will collect routine clinical data.*

We intend to collect demographic and clinical data from patients' medical records that include, but are not limited to: HF, NID, age, sex, level of education, marital status at enrollment in HIV care, date of enrollment in HIV care, date of ART initiation, ARV, Body mass index (BMI), CD4+ T-cell count, HIV-1 viral load (VL) (data and value), WHO clinical stage at the first visit and ART initiation, hemoglobin and full blood count on the date of enrollment in HIV care (or nearest), residence (urban or rural), and records of ART pick-ups (to assess retention) (**Appendix 9**). Data will be extracted from the electronic patient tracking system OpenMRS, that stores clinical information from the medical records of PLHIV registered at the health facility.

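### The Timeline lets the patient baseline survey overlap with training at the three intervention sites, so comparisons that use that baseline could be biased toward no effect

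*Combined protocol and SAP*

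**What the plan says.** Section 15 (Timeline) gives "Months 1-2 & Months 6-7" for patient survey recruitment. It describes the two rounds as run "via baseline (study start) and end-line (approximately 6 months after study start) surveys". The row above, labelled Months 1-4, holds the sessions of all three intervention arms, for example "Resilience/Wellness Intervention arm sessions; held bi-monthly". Recruitment and baseline assessment of health care workers are both placed in Month 1.

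Section 8.a sets the length of each course. For resilience: "The training course will occur every other week and consist of 4 sessions of 60-120 minutes each". For anti-stigma: "The training will occur once every other week, for at least 4 sessions of 60-120 minutes each".

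For patients, Section 8.a defines the rounds as "one at baseline (i.e., study initiation) and one at endline (i.e., at 6-7 months after study initiation". The reference point is the start of the study, not a site's first session. The same section states that "different PLHIV participants can be recruited at the two time points", so the baseline round serves mainly as a site-level reference.

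Section 10 (Objective 2) says most analyses will resemble those of Objective 1, whose outcomes are changes from baseline. It does not say how the baseline patient survey enters the model.

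**The concern.** The patient questionnaires in Appendix 2 ask whether providers listen, explain and show respect, and whether people with HIV are treated worse. Tables 2 and 3 show sessions on communication and stigma, so the sessions aim to change what the survey measures. Patients are recruited as they leave a care visit. A patient interviewed in Month 2 at a trained site may therefore be describing staff who have already attended sessions.

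This cannot happen at the control site, so any contamination of the baseline differs by arm. If training works, the baseline at trained sites is already shifted in the direction of benefit, and a change from that baseline understates the effect.

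With one facility per arm, randomization cannot be relied on to balance existing differences between sites. The baseline round is the main means of allowing for them in the survey outcomes.

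**Working it through.** **Inputs.** Baseline window: Months 1-2, taken as 61 days or 8.7 weeks (Section 15). Session window: Months 1-4, about 17.4 weeks (Section 15). Four sessions two weeks apart (Section 8.a). Survey size and detectable differences: 80 per facility; 0.55, 0.71 and 0.96 SD at ICC 0.025, 0.05 and 0.10 (Section 7.c).

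**Session frequency.** The Timeline's word for frequency could mean every two months, but that allows only about two sessions in four months. Only the twice-a-month reading agrees with Section 8.a.

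**1. The plan's own figures.** Take two sites against two, with 160 surveys per side and design effect 1 + 79 × ICC = 2.975, 4.95, 8.9. Effective n per side = 160 / design effect = 53.8, 32.3, 18.0. A two-sample t calculation at 80% power gives 0.545, 0.708 and 0.962 SD. The stated figures reproduce.

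**2. Course length.** Four fortnightly sessions span 3 × 2 = 6 weeks (42 days). A course ends inside the baseline window if it starts by 8.7 − 6 = 2.7 weeks (about day 19). It ends inside Months 1-4 if it starts by 17.4 − 6 = 11.4 weeks.

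**3. Overlap by start date.** Assume interviews are spread evenly over 8.7 weeks, with sessions at weeks s, s+2, s+4 and s+6.

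- Share of interviews after session 1 = max(0, 8.7 − s) / 8.7.
- Mean share of the course already delivered = Σ max(0, 8.7 − t) / (4 × 8.7), summed over the four session times t.

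| First session (week) | Interviews after session 1 | Mean share of course delivered |
|---|---|---|
| 0 | 100% | (8.7 + 6.7 + 4.7 + 2.7) / 34.8 = 66% |
| 2 | 77% | (6.7 + 4.7 + 2.7 + 0.7) / 34.8 = 43% |
| 4 | 54% | (4.7 + 2.7 + 0.7) / 34.8 = 23% |
| 6 | 31% | (2.7 + 0.7) / 34.8 = 10% |
| 8 | 8% | 0.7 / 34.8 = 2% |
| after 8.7 | 0% | 0% |

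Counting in whole days gives 64%, 41% and 20% for starts on days 1, 15 and 31. If the combined arm runs its two courses one after the other (8 sessions, 98 days), the mean share with a day-1 start is 33%.

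**4. Effect on a change contrast.** If a share f of the effect is present at baseline, the change shows (1 − f) of it. The true effect needed to produce a stated detectable difference d is d / (1 − f). The values of f below are illustrative.

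| f | True effect needed (SD) | Power at the stated differences |
|---|---|---|
| 0 | 0.55 / 0.71 / 0.96 | about 81-82% |
| 0.10 | 0.61 / 0.79 / 1.07 | about 73% |
| 0.25 | 0.73 / 0.95 / 1.28 | about 57% |
| 0.50 | 1.10 / 1.42 / 1.92 | about 30% |

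Power is by normal approximation on the effective n from step 1. The table shows attenuation only. It takes the plan's detectable differences as they stand and adds no variance for a second survey round.

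**The case against.** Much of the case on the other side stands.

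- **The overlap is possible, not certain.** A reader might infer that part of the training effect is necessarily in the baseline, or that only the control site has a genuine pre-training round. The documents do not support that. The Timeline works in whole months, both definitions of baseline point to the start of the study, and a site could finish its interviews before session 1. What stands is that nothing requires it to.
- **A minimum loss of 23% cannot be claimed.** Considering only starts at weeks 0 to 4 might suggest a loss of 23-66%. The session row permits later starts, so the range is about 0-66%. The week-0 figure is also hard to reach, because Month 1 must hold recruitment and baseline assessment of up to 100 health care workers.
- **Transfer to patients may be slow.** Some items, such as general mistrust or ever having been treated unfairly, reflect accumulated experience. Any lag reduces the loss.
- **The affected contrast is not defined.** Section 10 does not specify an endline-minus-baseline analysis of the surveys. Its Objective 2 covariate list omits the baseline outcome, which the Objective 1 list includes. The reference back to analyses of change makes use of the baseline plausible but does not settle it.
- **The outcomes are not the leading ones.** Section 8.b makes adherence, retention and viral load from records the primary measure for patients, and Section 7.c calls the patient surveys exploratory.

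These points limit the size and reach of the problem. They do not remove it: followed as written, the schedule permits an overlap that can bias one set of comparisons, and only at trained sites.

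**Conclusion.** The concern holds in conditional form. The schedule allows patient baseline interviews to fall after training has begun at the three intervention sites. If the baseline round is used in the analysis, effects on satisfaction, mistrust and perceived provider stigma could be biased toward no effect.

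At a single-training site the possible share runs from 66% of the course (first session at week 0) to 0% (first session after the window closes). These figures assume evenly spread interviews and an immediate effect proportional to sessions delivered. They fall if effects lag, and the combined arm's share is smaller if its courses run in sequence. The direction assumes that training works as intended.

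This is worth correcting because the remedy is simple and the design offers little else to separate training from site.

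**What to change.** **If baseline collection has not finished.** In Section 8.a (patient survey procedures) and Section 15, require each site's baseline patient surveys to be completed before that site's first session, with the control site surveyed over the same dates. There are two ways to do this:

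- Close the survey earlier, within Month 1 and before sessions begin.
- Start sessions later within Months 1-4. A four-session course starting at week 8.7 ends at week 14.7, inside the 17.4-week window. Two courses in sequence span 14 weeks and must start by about week 3.4, so if the combined arm works that way the survey must close early instead.

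State in Section 10 whether the survey outcomes are analysed as change, with baseline adjustment, or at endline only. The cost is scheduling, with no added participants or items. Starting later also shortens the gap between training and the endline survey.

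**If baseline collection is over.** Appendix 4 already reports moral injury results from a scale given only at baseline, which suggests this may be so. Compare interview dates with session dates, report how many baseline surveys per site precede session 1, and use only those as the site baseline. If few remain, make this a sensitivity analysis.

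The cost is precision. Under the even-spread assumption, 0%, 23%, 46%, 69% or 92% of a trained site's baseline surveys would remain for a first session at week 0, 2, 4, 6 or 8.

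Two facts need checking first:

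- **Interview dates.** Appendix 2 lists no interview date, and Section 10 allows paper forms to be entered later, so an entry date may not be the interview date.
- **Number per round.** Section 7.c gives 80 surveys per facility (320 in all), and Section 15 gives 320 across both windows. Neither says how many belong to the baseline round.

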## Appendix 1: Survey Questions (Objective 1: HCW surveys)

### **Sociodemographic data (only to be collected at baseline survey)**

- a. Age (years)
- b. Sex
- c. Marital status
- d. Language knowledge – perception and speaking
- e. Highest level of education
- f. Category of role/position at the health facility
- g. How long have you been working as a health care professional (years, months if <12 months)
- h. How long have you been working in this health facility (years, months if <12 months)
- i. Are you contracted by the National Health System (NHS) or a non-governmental organization (NGO)?

### **Measures for the HCW**

#### Resilience

Response categories: Strongly Disagree, Disagree, Neutral, Agree, Strongly Agree

1. I can enjoy my personal time without focusing on work matters.
2. I am able to disconnect from work communications during my free time (emails/phone, etc.).
3. I lose sleep over work issues.
4. I am able to free my mind from work when I am away from it.
5. I see every patients/client as an individual person with specific needs.
6. I care for all my patients equally even when it is difficult.
7. My work is meaningful.
8. The work I do makes a real difference.

### HIV stigma (Provider Stigma)

Response categories: Strongly Disagree, Disagree, Neutral, Agree, Strongly Agree

1. People living with HIV could have avoided HIV if they had wanted to
2. HIV is punishment for bad behavior
3. Most people living with HIV do not care if they infect other people
4. People living with HIV should feel ashamed of themselves
5. Most people living with HIV have had many sexual partners
6. People get infected with HIV because they engage in irresponsible behaviors

#### Anticipated Shame

7. I would be ashamed if I were infected with HIV
8. I would be ashamed if someone in my family were infected with HIV

### Burnout

Response categories: i) "Always or to a very high degree"; ii) "Often or to a high degree"; iii) "Sometimes or somewhat seldom or to a low degree"; iv) "Never/almost never or to a very low degree"

#### Personal burnout

1. How often do you feel tired?
2. How often are you physically exhausted?
3. How often are you emotionally exhausted?
4. How often do you think: "I can't take it anymore"?
5. How often do you feel worn out?
6. How often do you feel weak and susceptible/vulnerable to illness?

#### Work-related burnout

1. Do you feel worn out at the end of the working day?
2. Are you exhausted in the morning at the thought of another day at work?
3. Do you feel that every working hour is tiring for you?
4. Do you have enough energy for family and friends during leisure time? (inverse scoring)
5. Do you find that your work is emotionally exhausting?
6. Does your work frustrate you?

7. Do you feel burnt out because of your work?

Client-related burnout

1. Do you find it hard to work with patients?
2. Does it drain your energy to work with patients?
3. Do you find it frustrating to work with patients?
4. Do you feel that you give more than you get back when you work with patients?
5. Are you tired of working with patients?
6. Do you sometimes wonder how long you will be able to continue working with patients?

*Depersonalization*

Response categories: "Never, A few times a year or less," "Once a month or less," "A few times a month," "Once a week," "A few times a week," "Every day"

1. I have become more callous toward people since I took this job.

*Moral Injury Questionnaire (only at baseline)*

Moral Injury Symptom Scale: Healthcare Professionals Version (MISS-HF) The following questions may be difficult, but they are common experiences of busy healthcare professionals. They concern your experiences on your job as a health professional and how you are feeling now. Try to answer every question. Circle a single number between 1 (strongly disagree) and 10 (strongly agree) to indicate how much you personally agree or disagree with each statement.

- 1 = Strongly disagree
- 2 = Disagree
- 3 = Disagree somewhat
- 4 = Disagree a little bit
- 5 = Neutral (neither disagree nor agree)
- 6 = Agree a little bit
- 7 = Agree somewhat
- 8 = Agree
- 9 = Agree a lot
- 10 = Strongly agree

1. I feel betrayed by other health professionals whom I once trusted.
2. I feel guilt over failing to save someone from being seriously injured or dying.
3. I feel ashamed about what I've done or not done when providing care to my patients.
4. I am troubled by having acted in ways that violated my own morals or values.
5. Most people with whom I work as a health professional are trustworthy.
6. I have a good sense of what makes my life meaningful as a health professional.
7. I have forgiven myself for what's happened to me or to others whom I have cared for.
8. All in all, I am inclined to feel that I'm a failure in my work as a health professional.
9. I sometimes feel God is punishing me for what I've done or not done while caring for patients.
10. Compared to before I went through these experiences, my religious/spiritual faith has strengthened.
11. Do the feelings you indicated above cause you significant distress or impair your ability to function in relationships, at work, or other areas of life important to you? In other words, if you indicated any problems above, how difficult have these problems made it for you to do your work, take care of things at home, or get along with other people?

Depression (only at endline) – response categories for 1-9 (not at all, several days, more than half the days, nearly every day)

Over the last two weeks, how often have you been bothered by any of the following problems:

1. In the last two weeks, how many days have you had little interest or pleasure in doing things?
2. In the last two weeks, how many days have you felt down, depressed, or hopeless
3. In the last two weeks, how many days have you had trouble falling or staying asleep, or sleeping too much.
4. In the last two weeks, how many days have you felt tired or having little energy.
5. In the last two weeks, how many days have you had poor appetite or overeating.
6. In the last two weeks, how many days have you felt like you do not like yourself, that you are a failure / not useful / have no worth or that you let yourself or your family down.

7. In the last two weeks, how many days have you had a lack of concentration in doing things, such as working, studying, home chores, or other activities.
8. In the last two weeks, how many days have you moved or spoken so slowing that other people have noticed. Or the opposite – being so fidgety or restless that you have been moving around a lot more than usual.
9. In the last two weeks, how many days have you thought that you would be better off dead, or of hurting yourself.
10. If you checked off any problems. How difficult have these problems made it for you to do your work, take care of things at home or get along with other people? (Not difficult at all, somewhat difficult, very difficult, extremely difficult)

Anxiety (only at endline) response categories for 1-7 (not at all, several days, more than half the days, nearly every day)

Over the last two weeks, how often have you been bothered by the following problems?

1. Feeling nervous, anxious, or on edge
2. Not being able to stop or control worrying
3. Worrying too much about different things.
4. Trouble relaxing
5. Being so restless that it is hard to sit still
6. Becoming easily annoyed or irritable
7. Feeling afraid, as if something awful might happen.

8. If you checked off any problems. How difficult have these problems made it for you to do your work, take care of things at home or get along with other people? (Not difficult at all, somewhat difficult, very difficult, extremely difficult)

Suicidality (Response categories yes/no)

1. In the last 30 days, have you thought it would be better or be dead or have you wished you were dead?
2. In the last 30 days have you thought of a way to commit suicide.
3. In the last 30 days, have you attempted suicide?
4. Have you ever made any suicide attempts throughout your life?

